### 6.6.2 Paternal exposure

Male subjects should refrain from fathering a child or donating sperm during the study and 3 months following the last dose.

## 6.7 Management of investigational product-related toxicities: Dose reductions

Dose reductions are not permitted in this study.

## 7. INVESTIGATIONAL PRODUCT AND OTHER TREATMENTS

### 7.1 Identity of investigational product(s)

All investigational products will be supplied to the investigator by AstraZeneca in tablet formulation for oral use.

Investigational product	Dosage form and strength	Manufacturer
Rosuvastatin	20 mg tablets a	AstraZeneca
Placebo	Matching placebo tablets a	AstraZeneca

a. The lot number will be identified in the clinical study report. Rosuvastatin (CRESTOR) Clinical tablets for use in clinical trials are identical to CRESTOR commercial tablets in all aspects with the exception of the tablet markings. CRESTOR Clinical tablets are plain (unmarked), while commercial tablets are marked (intagliated).

### 7.2 Dose and treatment regimens

At Visit 4 (Week 0), the subject will be randomized to either rosuvastatin 20 mg or placebo. Beginning at Visit 4, subjects will take the investigational product orally with water once daily for the duration of the 104-week treatment period. Each dose will consist of 1 tablet. The subject should be encouraged to take the investigational product at the same time each day.

### 7.3 Labelling

The investigational product will be supplied in subject-specific labelled bottles. Each labelled bottle will contain sufficient medication for at least each treatment period plus overage.

Labels will be prepared in accordance with Good Manufacturing Practice (GMP) and local regulatory guidelines. The labels will fulfill GMP Annex 13 requirements for labelling. Label text will be translated into local language.

### 7.4 Storage

All investigational products must be kept in a secure place under appropriate storage conditions, as specified on the investigational product label on each bottle.

The investigational product must be stored in its original container in a lockable storage facility until dispensed to the subjects and should be protected from light and moisture. The investigational product must be stored below 25°C and should not be frozen.

## 7.5 Compliance

Subjects must return all unused medications and empty containers to the investigator. The number of tablets returned at Visits 5 (Week 6), 6 (Week 13), 7 (Week 26), 8 (Week 39), 9 (Week 52), 10 (Week 65), 11 (Week 78), 12 (Week 91) and 13 (Week 104) must be checked against the number of tablets dispensed to determine subject compliance.

Compliance will be calculated, as follows:

$$\% \text{ Compliance} = \frac{\# \text{ of tablets dispensed} - \# \text{ of tablets returned}}{\# \text{ of days between visits} \times \# \text{ of tablets per daily dose}} \times 100$$

A subject should be counselled on the importance of taking his or her medication as prescribed. Any subject taking less than 80% of the prescribed investigational product at 2 consecutive visits will be considered non-compliant. The subject will continue in the study but will be counselled on the importance of taking his or her medication regularly.

In cases where a subject is removed from treatment for 2 weeks or longer, the AstraZeneca physician must be contacted prior to resuming therapy.

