**Table 1 Study plan**

Study plan	Screening			Treatment									
	1	2	3	4	5	6	7	8	9	10	11	12	13/ET a
Week number*	-6	-4	-2	0	6	13	26	39	52	65	78	91	104
Informed consent	√												
Randomization				√									
Vital signs	√			√	√	√		√		√		√	√
Height	√												
Body weight	√			√									√
Adverse events	√	√	√	√	√	√	√	√	√	√	√	√	√
Concomitant medications	√			√	√	√	√	√	√	√	√	√	√
Medical history	√												
Physical examination				√									√
ECG				√									√
Chemistry panel	√ b			√	√	√		√ c		√ c		√ c	√
Pregnancy test d	√												
Hematology				√									√
Urine sample e				√									√
Serum lipid profile	√			√	√	√		√		√		√	√
ApoA-I and ApoB				√									√
Risk assessment	√												
IMT		√ f	√ f				√		√		√		√ g
Dispense investigational product				√		√	√	√	√	√	√	√	
Investigational product compliance					√	√	√	√	√	√	√	√	√
TLC counselling h	√			√	√	√	√	√	√	√	√	√	

ALP Alkaline phosphatase; ALT Alanine aminotransferase; Apo Apolipoprotein; AST Aspartate aminotransferase; CK Creatine kinase; ECG Electrocardiogram; ET Early termination; IMT Intima-media thickness; TLC Therapeutic Lifestyle Changes; TSH Thyroid stimulating hormone.

\* Note: The visit window for visits 5-13 is ±7 days.

a In the event of early termination, all non-IMT procedures scheduled for Visit 13 (Week 104) are to be conducted. A single IMT is to be performed on any subject who withdraws after 26 weeks.

b Including TSH at Visit 1.

c Abbreviated chemistry panel including liver function tests (ALT, AST, bilirubin, ALP), serum creatinine, and CK only.

d Urine pregnancy test conducted at study site. Required only for premenopausal females. Those with amenorrhea for at least 1 year are exempt.

e For complete urinalysis.

- f IMT measurements at Visit 2 (Week -4) and Visit 3 (Week -2) must meet inclusion criteria of maximum IMT  $\geq 1.2$  mm and  $< 3.5$  mm.
- g Final IMT procedures will be scheduled before discontinuation of study treatment. The second and final IMT procedure should occur at or before Visit 13 (Week 104), at the time of discontinuation of the study treatment. The 2 IMT procedures for Visit 13 should be performed on different days when possible.
- h TLC counselling is to be reinforced at each clinic visit.

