#### **4.2.2 Visit 5 (Week 6)**

Subjects will be required to fast for 8 hours (water permitted) prior to Visit 5 (Week 6). Those subjects who have failed to fast for 8 hours should return for their blood draw following an 8-hour fasting period. At the visit, the following procedures will be performed:

- Recording of vital signs
- Recording of AEs
- Recording of concomitant medications
- Chemistry panel
- Serum lipid profile
- Investigational product compliance
- TLC counselling

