#### **4.2.10 Visit 13 (Week 104)**

Subjects will be required to fast for 8 hours (water permitted) prior to Visit 13 (Week 104). Those subjects who have failed to fast for 8 hours should return for their blood draw following an 8-hour fasting period. If, at the final visit, the subject has failed to fast, the subject should remain on investigational product until the blood samples have been drawn.

At this last visit during the treatment period (Visit 13), the following procedures will be performed:

- Recording of vital signs
- Measurement of body weight
- Recording of AEs
- Recording of concomitant medications
- Physical examination
- ECG
- Chemistry panel
- Hematology

- Urine sample for complete urinalysis
- Serum lipid profile
- ApoA-I and ApoB
- IMT (2 IMT procedures for Visit 13 are to be performed on different days when possible with the second IMT procedure occurring on or before Visit 13)
- Investigational product compliance

The final 2 IMT procedures will be scheduled before discontinuation of study treatment. The second of the final 2 IMT procedures will occur at or before Visit 13 (Week 104), at the time of discontinuation of the study treatment.

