## 7.6 Accountability

The investigational products provided for this study will be used only as directed in the study protocol. The investigational products are to be prescribed only by the investigator or his or her designee.

Subjects must return all unused medications and empty containers to the investigator. The study personnel will account for all investigational products dispensed to and returned from the subject.

The investigator must maintain accurate records to account for the receipt of the investigational materials. This record keeping consists of a dispensing record that includes the identification of the person receiving the medication, the date of dispensing, and any unused medication returned to the investigator. The dispensing record, in addition to any drug accountability information, must be recorded on the eCRFs. The delivery records must be able to be reconciled with records of usage and returned stocks. Any discrepancies must be reconciled. Certificates of delivery and returns must be signed by the investigator or responsible person.

The investigator will retain the returned medication until AstraZeneca-authorized personnel collect it, along with any trial treatments not dispensed. An AstraZeneca monitor will account for all investigational products received at the center, unused investigational products, and

appropriate destruction (according to local procedures). Certificates of destruction and/or return should be signed.

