6	
Enrolled, even though subject met the exclusion criteria below:
 
Use of pharmacologic lipid-lowering medications (eg, statins, fibrate derivatives, bile acid binding resins, niacin or its analogues at doses > 400 mg or prescribed Chinese traditional drugs), including cholesterol-absorption inhibitors (CAIs), and CAI/statin combination, within 12 months prior to Visit 1 (Week -6)
	Complete data exclusion.
	Major deviations:	
8	Overall compliance during the double-blind treatment period <80% of the prescribed drug	Complete data exclusion.

Number	Important protocol deviations / Criteria	Complete/partial data exclusion
9	Use of prohibited/disallowed medication during the double-blind treatment period (medications with an ATC code of C10AA, C10, or C10AX or 'Reason for Therapy' is recording on the eCRF as 'Control for dyslipidemia', 'Hyperlipidemia' or 'Hypolipidemic' are only considered disallowed if they are used for more than 3 months across the study period before last dose date).	Partial data exclusion: Data at the affected visit and subsequent visits will be excluded. These concomitant medications are the lipid lowering agents listed in appendix 7.7.1 of the protocol.
10	CIMT data from ultrasound scans taken more than 31 days after the last dose of study medication.	Partial data exclusion: Data at the affected visit and subsequent visits will be excluded.
11	Subject randomly allocated a treatment out of sequence or inadvertently receives the wrong treatment.	Complete data exclusion.

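### The protocol has tablets returned at Visit 5 (Week 6) and retained by the site but dispenses none until Visit 6 (Week 13), and the SAP compliance formula has no rule for a Visit 5 count of a kit still in use

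*Protocol*

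**What the plan says.** **Return and count.** Protocol 7.5 states "Subjects must return all unused medications and empty containers to the investigator". Its next sentence, which begins "The number of tablets returned at Visits 5 (Week 6), 6 (Week 13), 7 (Week 26), 8 (Week 39" and continues through Visit 13, has the returned tablets checked against those dispensed.

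**Retention.** Protocol 7.6 adds: "The investigator will retain the returned medication until AstraZeneca-authorized personnel collect it, along with any trial treatments not dispensed".

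**Dispensing.** In Table 1 the row "Dispense investigational product" is marked at Visit 4 and at Visits 6 to 12. Section 4.2.2 lists "Investigational product compliance" for Visit 5 and no dispensing; the next dispensing is in 4.2.3, at Visit 6.

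**Dosing and supply.** Protocol 7.2 requires one tablet a day from Visit 4 for 104 weeks. Section 7.3 says each bottle covers at least a treatment period plus overage, but gives no tablet number and does not define the period.

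**Analysis.** SAP 4.2.5.3 computes one overall figure: total dispensed minus total returned, divided by the days from first dispensing to last return. It has rules for missing returns and missing return dates, but none for two returns of the same kit. SAP Appendix A, item 8, removes a subject completely from the per-protocol set for "Overall compliance during the double-blind treatment period <80% of the prescribed drug".

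**The concern.** A site cannot follow all of these rules at Visit 5. If it takes the tablets back and keeps them, the subject cannot dose daily until Visit 6. If it hands the kit back, it takes a step that no passage describes, and there is no dispensing event to record it under.

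The second course matters for the analysis. A Visit 5 count entered as a return is part of the total returned in SAP 4.2.5.3, although most of those tablets are taken afterwards. Recorded compliance is then too low, and whether a subject stays in the per-protocol set depends partly on how the site did its bookkeeping. Protocol 8.5.7 names that set as the robustness check on the ITT result. The error is a fixed number of tablets, so it weighs most on subjects who stop early.

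**Working it through.** The plan gives no figure of its own to reproduce.

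**Inputs from the documents**
- Treatment period: 104 weeks = 728 days (Protocol 7.2).
- Visit 5 is day 42 and Visit 6 is day 91 (Table 1). The interval is 91 − 42 = 49 days, or 35 to 63 days with the ±7-day windows.
- Compliance formula: SAP 4.2.5.3. Limit: 80% (SAP Appendix A, item 8).

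**Assumptions, not in the documents**
- The Visit 4 supply is 91 tablets (13 weeks × 7) plus an overage *o* of 0 to 14.
- The kit is handed back at Visit 5 with no dispensing record, and the Visit 5 and Visit 6 counts are both entered as returns and summed.
- True compliance *p* is constant over time, and the last return is on the last day of treatment.

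**Base check.** If the Visit 4 kit is counted once, at Visit 6, a fully adherent completer scores 728/728 = 100% for any overage.

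**Step 1: the error.** Tablets left at Visit 5 = 91 + *o* − 42*p*. This count is the excess subtraction, so

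recorded compliance = *p* − (91 + *o* − 42*p*)/728.

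**Step 2: fully adherent completer (*p* = 1)**
- *o* = 0: 1 − 49/728 = 93.3%
- *o* = 14: 1 − 63/728 = 91.3%

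**Step 3: true compliance recorded as exactly 80%.** Solving step 1 for *p* gives *p* = (0.80 × 728 + 91 + *o*)/(728 + 42).
- *o* = 0: 673.4/770 = 87.5%
- *o* = 14: 687.4/770 = 89.3%

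A completer whose true compliance lies between 80% and these values is recorded below 80%.

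**Step 4: fully adherent subject who stops on day *d*, after Visit 6.** Recorded compliance = (*d* − 49 − *o*)/*d*.
- Week 26 (*d* = 182): 133/182 = 73.1% for *o* = 0; 119/182 = 65.4% for *o* = 14.
- Recorded compliance reaches 80% at *d* = (49 + *o*)/0.20, which is 245 days (Week 35) for *o* = 0 and 315 days (Week 45) for *o* = 14. Earlier stoppers fall below the limit.

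**Sensitivity to the assumed supply.** At *o* = 29 the completer scores 650/728 = 89.3% and the Week 26 stopper 104/182 = 57.1%.

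**After the fix.** With only the final return of each kit counted, the fully adherent subject scores 100% for every overage.

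**The case against.** **The supply was plainly meant to last to Visit 6.** Daily dosing in 7.2 and the bottle content in 7.3 point that way. The retention sentence in 7.6 also covers undispensed drug, so it can be read as end-of-use accountability. This stands. A reader might infer from the literal rules that subjects went 7 weeks (49/728 = 6.7% of the period) without drug. The documents do not support that; they show only that the text is contradictory.

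**The compliance error is conditional.** SAP 4.2.5.3 handles missing return dates kit by kit, kits carry unique numbers (Protocol 3.6), and 7.6 requires discrepancies to be reconciled. One return per kit would avoid the error, provided that it is the final one. This also stands, but no passage says that returns are recorded this way.

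**Are the same tablets subtracted twice?** A reader might infer this, but it is not the main mechanism. With no overage, nothing is left at Visit 6 for a fully adherent subject: the 49 tablets are subtracted once, wrongly, and then taken. Only leftovers still present at Visit 6 could appear in both counts.

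**Is the by-visit formula in Protocol 7.5 at stake?** Not for analysis. SAP 4.2.5.3 uses overall compliance only.

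**Does Visit 13 have the same clash?** It might seem so, because 4.2.10 says that if a subject has not fasted, "the subject should remain on investigational product until the blood samples have been drawn". But Protocol 5.1.2 has such a subject return within the visit window, so the return and count can take place when the visit is completed.

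**The consequence is limited.** SAP 4.3.4 treats the ITT results as definitive, and compliance does not enter them. A fully adherent completer stays in the per-protocol set under the assumptions used here.

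**Conclusion.** The contradiction at Visit 5 is real. Protocol 7.2, 7.5, 7.6, Table 1 and 4.2.2 cannot all be followed, and 7.3 does not settle the matter. It is a defect in the text and says nothing about what subjects actually received.

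The statistical consequence depends on whether the Visit 5 count was entered as a return of a kit that stayed in use, and the size depends on the assumed supply. Under those assumptions a completer's recorded compliance is about 7 to 9 points too low at full adherence. That matters only for completers with true compliance between 80% and roughly 87.5% to 89.3%. Early stoppers are hit harder: even full adherence does not keep a Week 26 stopper in the per-protocol set. The damage is confined to per-protocol membership and the supportive CIMT analyses; the ITT primary analysis does not change.

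**What to change.** 1. **Protocol.** Reconcile Table 1, 4.2.2, 7.2, 7.3, 7.5 and 7.6 on what happens to the Visit 4 supply at Visit 5. The sponsor should state the handling. By the protocol's own timetable (last subject completing in 1Q 2019 after 104 weeks, so randomised by about 1Q 2017), all Visit 5 dates had probably passed before Edition 2.0 of 28 Mar 2018. The clarification therefore mainly documents what sites did.
2. **SAP 4.2.5.3.** Count each kit once, using its final return only, so that a Visit 5 count of a kit still in use is not subtracted.
3. **Data check before unblinding.** List kits with two return records, and Visit 4 kits whose only return is dated Visit 5 in subjects who went on dosing. Resolve these before per-protocol membership is fixed.

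The cost is a short clarification, one line of SAP text with its programming, and one listing. No visits, drug or assessments are added.

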## 7.6 Accountability

The investigational products provided for this study will be used only as directed in the study protocol. The investigational products are to be prescribed only by the investigator or his or her designee.

Subjects must return all unused medications and empty containers to the investigator. The study personnel will account for all investigational products dispensed to and returned from the subject.

The investigator must maintain accurate records to account for the receipt of the investigational materials. This record keeping consists of a dispensing record that includes the identification of the person receiving the medication, the date of dispensing, and any unused medication returned to the investigator. The dispensing record, in addition to any drug accountability information, must be recorded on the eCRFs. The delivery records must be able to be reconciled with records of usage and returned stocks. Any discrepancies must be reconciled. Certificates of delivery and returns must be signed by the investigator or responsible person.

The investigator will retain the returned medication until AstraZeneca-authorized personnel collect it, along with any trial treatments not dispensed. An AstraZeneca monitor will account for all investigational products received at the center, unused investigational products, and

appropriate destruction (according to local procedures). Certificates of destruction and/or return should be signed.

## 7.7 Concomitant and other treatments

The administration of all medication (including investigational products) must be recorded in the appropriate sections of the eCRF. Introduction of new concomitant drugs should be recorded throughout the trial.

Other medication that is considered necessary for the subject's safety and well-being may be given at the discretion of the investigator and are acceptable, provided that these medications do not conflict with the exclusion criteria (Section 3.2).

Subjects must follow the medication restrictions outlined in the inclusion and exclusion criteria (Section 3.1 and Section 3.2, respectively) during the study.

### 7.7.1 Prohibited medications

With the exception of lipid-regulating drugs, the only other disallowed drugs will be cyclosporine and tacrolimus, azathioprine sodium, and other potent immunosuppressants as listed in Table 3 since use of these agents may increase the risk of AEs during treatment with rosuvastatin.

**Table 3 Disallowed concomitant medications**

Class of drug	Generic name
Lipid Regulation	niacin/nicotinic acid (includes vitamins/supplements with >50mg/day niacin/nicotinic acid) bile acid sequestrant probucol clofibrate fenofibrate gemfibrozil (and other fibrates) all statins, such as (but not exclusively) atorvastatin, lovastatin, pravastatin, rosuvastatin (except for study medication), simvastatin, and fluvastatin cholesterol-absorption inhibitor/ezetimibe cholestyramine cholesterol-absorption inhibitor and statins combination/vytorin any other prescription medicine given to treat dyslipidemia any other prescription medicine given for lipid lowering any food supplement taken specifically for lipid lowering
Immunosuppressants	azathioprine sodium tacrolimus cyclosporine
Protease inhibitors	all protease inhibitors

### **7.7.2 Warfarin (including warfarin derivatives and Coumadin)**

In 2 clinical studies, one in normal volunteers and the other in subjects receiving a coumarin anticoagulant, rosuvastatin potentiated the effect of the coumarin anticoagulant. With rosuvastatin and other HMG-CoA reductase inhibitors, clinically evident bleeding and/or increased prothrombin time has been reported in a few subjects taking coumarin anticoagulants concomitantly.

For this reason, careful monitoring of international normalized ratio (INR) is required when warfarin and blinded investigational product are co-administered at any time during the subject's participation during this trial. It is suggested that the investigators should, in accordance with usual practice, measure INR frequently until warfarin dose stabilization is achieved, and periodically thereafter in the following situations:

- when starting warfarin therapy in a randomized subject
- when a subject already receiving warfarin begins randomized trial treatment

To provide current information and advice, investigators should telephone their study monitor to discuss the situation with the AstraZeneca Study Team Physician.

### **7.7.3 Other concomitant treatment**

Other medication other than that described above, which is considered necessary for the subject's safety and well-being, may be given at the discretion of the investigator and recorded in the appropriate sections of the eCRF.

## **8. STATISTICAL ANALYSES**

### **8.1 Statistical considerations**

All personnel involved with the analysis of the study will remain blinded until database lock and protocol violators are identified.

Analyses will be performed by AstraZeneca or its representatives.

A comprehensive Statistical Analysis Plan will be prepared and any subsequent amendments will be documented, with final amendments completed prior to unblinding of the data.

### **8.2 Sample size estimate**

CCI

## 8.3 Definitions of analysis sets

### 8.3.1 Efficacy analysis sets

Two analysis sets will be used for efficacy evaluation:

- The Intent-to-Treat (ITT) population consists of all randomized subjects. Subjects will be analyzed according to the treatment randomized.
- The per-protocol (PP) population is a subset of the ITT population that includes subjects without any important protocol deviations. The criteria for important protocol deviations will be defined in the statistical analysis plan. Subjects will be analyzed according to the treatment actually received.

The ITT population will be the primary efficacy analysis population. The CIMT analysis will be performed based on both the ITT and PP populations, and lipid and apolipoprotein analyses will be performed on the ITT population only.

